5.7.5 Administrative Data – Mental Health Diagnoses and Utilization

Programmers at our Minneapolis site will use the EMR to obtain the number of mental health clinic visits in the 12 months following study enrollment by each participant and to obtain a list of mental health diagnoses in each participant's EMR in the 12 months prior to study enrollment. The programmers will use this list to assign to each patient a primary mental health diagnosis using methods recommended by the MH QUERI. Primary mental health diagnosis will be defined as the most frequently occurring diagnosis at MH encounters during the 12 months prior to enrolling in the trial. For example, if a patient had three schizophrenia diagnoses and two schizoaffective diagnoses, s/he would be assigned the diagnosis of schizophrenia. We will then assign one of six main diagnostic categories to each participant based on their primary diagnosis: affective disorders, substance abuse disorders, non-PTSD anxiety disorders, PTSD, schizophrenia disorders, or other diagnoses.

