5.6 STUDY GROUPS

INTERVENTION

Telephone Counseling

Within one week of receiving a completed baseline survey, a counselor will phone intervention participants. Up to 6 contact attempts will be made at different times (i.e., morning, afternoon, evening) during the week. The purpose of the outreach call is to: 1) deliver motivational enhancement to quit smoking, 2) promote self-efficacy, and 3) encourage participants to participate in smoking cessation treatment. The full telephone counseling protocol is characterized by:

- *Motivational enhancement* – We will include motivational enhancement in each of the first several telephone calls and as-needed during later calls to increase patient motivation to quit and reduce relapse.

- ❑ *Multiple sessions* – Participating smokers will receive 8 calls over two months and then, for those who quit in this timeframe, monthly maintenance calls for six months. The initial call will be 30-45 minutes and subsequent calls will be 10-20 minutes.
- ❑ *Relapse-sensitive scheduling* – Participants will receive 4 calls to plan a quit date, three calls in the first two weeks after their Quit Date, when the relapse risk is highest, followed by another call in another two weeks. Patients who are quit at the 8 week call will receive monthly maintenance calls to work through any slips or barriers to continued abstinence.^{11,12}
- ❑ *Problem-solving therapy* – This approach, based on helping the smoker identify and solve expected and actual challenge, is endorsed by the national smoking cessation guidelines.¹³
- ❑ *Stress Reduction* – Our previous work providing tobacco cessation counseling to VA mental health patients identified stress and anxiety as a major barrier toward quitting and long-term abstinence among this population. Our counseling protocol includes stress reduction techniques, such as relaxation and mindfulness exercises,^{11,12} and the incorporation of smoking schedules to remove the link between smoking and stress responses.¹⁴ We will also send stress reduction self-help materials to intervention participants that the counselors will discuss during the counseling.

Medication Requests

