All smokers in the intervention arm will be asked about their NRT preference during their first counseling call. Their counselor will place a View Alert in CPRS for their facility's smoking cessation program or regular primary care provider indicating that the participant expressed interest in receiving NRT and their preference. The View Alert will also contain relevant information from the US Public Health Services guidelines for the treatment of tobacco. The counselors will monitor the participants' EMR for whether a prescription is written. If no prescription is written within 1 week after sending the View Alert, the counselor will place a follow-up View Alert reiterating the participant's expressed interest in NRT. The regular smoking cessation providers will not be required to prescribe or be required to prescribe the patient's preferred NRT. Rather, study staff will simply notify the providers that the patient expressed interest in receiving NRT. The Intervention counselors will also encourage participants to discuss NRT use with their regular providers.

Engaging MH Providers in the Treatment Process

In recognizing that a patient's regular Mental Health providers are an important source of support and treatment encouragement for our patient population, we will engage all intervention patients' primary mental health providers into the treatment process by alerting the providers of their patients' progress via CPRS progress notes and providing them information via email about the program and how they can support their patients. As we have done with [name] prior studies, the study's counselors will place a progress note into CPRS for each patient documenting the first counseling call and the quit plan developed during that call. Additional progress notes will be entered into the medical record when the patient quits smoking, when there is a significant change in the quit plan, and when the patient is discharged from the program. On each note, the patient's primary Mental Health provider (identified on the baseline survey and confirmed with EMR review) and psychiatrist (if different from the primary provider) will be added as an additional signer to the note. This process will also ensure the safety of participants using antipsychotic medications by notifying their psychiatrist of their quitting process.

CONTROL GROUP (USUAL VA CARE)

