5.7 DATA COLLECTION

All participants will be surveyed by mail at baseline, by mail 2 weeks after enrollment, and by telephone (or mail for non-respondents) at 6 and 12 months from enrollment. Research assistants will make up to 10 attempts at different days and times to reach participants by phone for the 6 and 12 month surveys. If we cannot reach a participant after 10 attempts, we will mail a paper version of the survey with a cover letter (Appendix K) to participants. Patients will receive a \$10 payment as reimbursement for completing each survey.

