8.0 SAFETY MONITORING AND REPORTING

Potential Risks

The intervention treatment being delivered in this study (counseling) is already shown to be effective and approved by the VA for use without informed consent. The main risk in this study is a breach of confidentiality similar to the risk incurred during a normal visit for care.

Surveillance and Reporting Procedures

In order to ensure patient safety, we will use the same approach we are using for our ongoing VA studies. We will monitor the following events:

Adverse events (AEs):

- Violations of confidentiality
- ER visits without hospitalization
- Suicidal ideation not requiring intervention

Serious adverse events (SAEs):

- Death
- Life-threatening event
- Hospitalization
- Suicidal ideation requiring intervention

Any AE that the research staff thinks may be related to study participation will be reported to a PI within 24 hours. If the PI is unavailable, the research staff will report it to the Project Director. The PI or Project Director will determine whether the event is a) serious or non-serious and b) anticipated or unanticipated. The PI or Project Director will ensure that any necessary actions are taken immediately to address the current patient situation, and then will decide if the team needs to make any changes in the protocol and/or consent forms to prevent future occurrences or better inform future participants. We will report the event to the IRB and DSMB as per VHA Handbook 1058.01 requirements.

In the case of suicidal or homicidal ideation, we will follow a protocol used on previous studies. We will train each person who contacts participants (tobacco cessation counselors and research assistants) in appropriate methods for assessing risk, conversing with participants, and completing a 'warm-transfer' to the VA National Suicide Prevention Hotline if a patient reports suicidal or homicidal ideation, plan or intent during counseling or a telephone survey. Clinicians (either [name], a VA primary care physician, or the counseling supervisor, [name], a VA clinical psychologist) will also be informed to evaluate cases and provide any further advisement or follow-up with patients' primary mental health providers.

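### Section 8.0 promises to monitor ER visits, hospitalizations, deaths and suicidal ideation, but the visible plan names no source that collects them equally in both arms

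*Combined protocol and SAP*

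**What the plan says.** Section 8.0 states "We will monitor the following events". The adverse events listed are confidentiality breaches, ER visits that do not lead to admission, and suicidal ideation that needs no intervention. The serious ones are death, life-threatening events, hospitalization, and ideation that does need intervention. On method, the section says only "we will use the same approach we are using for our ongoing VA studies". The reporting rule is: "Any AE that the research staff thinks may be related to study participation will be reported to a PI within 24 hours". Suicidal or homicidal ideation is acted on "if a patient reports suicidal or homicidal ideation, plan or intent during counseling or a telephone survey".

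For follow-up data, section 5.7.5 has programmers "use the EMR to obtain the number of mental health clinic visits in the 12 months following study enrollment". Sections 5.7.1 to 5.7.3 describe the surveys, which go to all participants: after baseline, "by mail 2 weeks after enrollment, and by telephone (or mail for non-respondents) at 6 and 12 months from enrollment".

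Staff contact outside the surveys is in section 5.6. In PRO, a counselor makes an outreach call, and then: "Participating smokers will receive 8 calls over two months and then, for those who quit in this timeframe, monthly maintenance calls for six months". Also in PRO: "The counselors will monitor the participants' EMR for whether a prescription is written". The control group is posted a list of local cessation services and otherwise receives usual care.

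**The concern.** A commitment to monitor events needs a source that would record them. Here the commitment is in section 8.0 and the sources are in sections 5.6 and 5.7, and they do not meet. What is left is what a participant happens to tell staff, or what a counselor happens to see in a chart, and both occur more often in PRO. The reporting trigger adds to this. Staff must think an event may be related to taking part, a judgment that is harder to make about someone who was only posted a list.

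Two things are at stake. First, any table of admissions, ER visits or deaths by arm would mix event rates with opportunity to be noticed. The plan itself has a safety interest here: section 2.0 treats the belief that cessation treatment worsens psychiatric conditions as mistaken, and section 5.6 refers to the safety of participants on antipsychotics. Second, section 6.0 imputes a 12-month outcome for each non-respondent by drawing from respondents. A participant whose death is not recorded would be handled the same way and could be imputed as abstinent.

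**Working it through.** **Step 1: sources set against the promised events.**

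| Source | Arms | What it records | Section 8.0 events |
|---|---|---|---|
| Surveys (5.7.1–5.7.3) | Both | Smoking, attitudes, alcohol and drug use, comorbidity, Kessler-6, Hospital Anxiety and Depression Scale | No item described |
| EMR extract after enrollment (5.7.5) | Both | Count of mental health clinic visits | None |
| Survey calls at 6 and 12 months | Both | Survey answers | If volunteered |
| Outreach and counseling calls (5.6) | PRO | Counseling content | If volunteered |
| Chart checks (5.6) | PRO | Prescriptions | Only if noticed |

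No row is a planned source, in both arms, for admissions, ER visits, deaths or ideation.

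**Step 2: planned live calls.** Inputs from section 6.0 are 1,920 per arm, 20% accepting counseling, and a 16% quit rate among those counseled, used here as the share who receive maintenance calls. Section 5.6 gives 8 calls plus 6 monthly calls for quitters. For those who accept, the outreach call is taken as the first of the eight.

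- Plan's own figure: 0.20 × 1,920 = 384, as stated. Decliners: 1,920 − 384 = 1,536.
- Control: 1,920 × 2 survey calls = 3,840.
- PRO, low (no maintenance calls, no decliner reached): 3,840 + 384 × 8 = 3,840 + 3,072 = 6,912. Ratio 6,912 / 3,840 = 1.8.
- PRO, high (maintenance calls, every decliner reached once): 6,912 + 384 × 0.16 × 6 + 1,536 = 6,912 + 369 + 1,536 = 8,817. Ratio 8,817 / 3,840 = 2.3.
- Share of the excess that falls on the 384 counseled: all of it in the low case; (3,072 + 369) / (8,817 − 3,840) = 3,441 / 4,977 = 69% in the high case.
- Per person: 10 to 16 calls if counseled, 2 or 3 for a PRO decliner, 2 in control.
- Before month 6, without maintenance calls: 3,072 to 4,608 in PRO against 0 scheduled in control.

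These counts assume completion. If only half of the eight calls took place and no decliner was reached, PRO would have 3,840 + 384 × 4 = 5,376, a ratio of 1.4.

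**Step 3: what unequal contact could do to counts.** This illustration rests on assumptions that are not in the documents: the same true event rate in both arms, each call uncovering an event independently with probability d, 10 calls for the counseled and 2 for everyone else, and timing ignored. Each participant counts at most once.

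- Recorded ratio = 0.8 + 0.2 × [1 − (1 − d)^10] / [1 − (1 − d)^2]. It does not depend on the event rate.
- d = 0.1: 0.8 + 0.2 × 0.651 / 0.19 = 1.49.
- d = 0.2: 0.8 + 0.2 × 0.893 / 0.36 = 1.30.
- d = 0.3: 0.8 + 0.2 × 0.972 / 0.51 = 1.18.
- At an assumed 10% event rate: about 54 against 36 recorded events (d = 0.1), or 116 against 98 (d = 0.3), with no true difference.

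**Step 4: deaths.** Section 6.0 draws an outcome for each non-respondent from respondents in the same propensity substratum, and describes no step that first identifies deaths. The documents give no mortality figure, so the size of this effect is not estimated.

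**The case against.** The strongest reply is that the plan does measure mental health in both arms. Kessler-6 and the Hospital Anxiety and Depression Scale are given to everyone at 2 weeks, 6 months and 12 months. Distress and active substance abuse are a named secondary outcome, research assistants are blinded, and mental health visits are counted for everyone over the full 12 months. This stands. A reader might infer that the trial could say nothing about harm, and the documents do not support that.

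Section 6.0 plans no between-arm test of adverse events, and section 8.0 describes operational reporting to the PI, IRB and DSMB. That also stands, so no planned test is biased. It does not supply a source for events that the plan says it will monitor, and any counts shown by arm would still carry the imbalance.

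The absence also cannot be proved. The survey instruments, the appendices and part of section 4.0 are not in the text available, and the approach of the team's ongoing studies is not described. Section 5.9 lists utilization in general terms and section 9.0 permits administrative follow-up data. The supportable statement is that the visible text specifies no source. A permission to collect data is not a specified extract, although it makes the repair easier.

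Finally, calls are not the only route. Chart checks exist, participants may contact the study, and survey callers in both arms are trained to handle suicide risk. Control events are therefore not wholly unseen. The chart route, however, is specified for PRO only and so widens the gap.

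**Conclusion.** The point holds in a limited form. As visibly specified, admissions, ER visits, deaths and suicidal ideation have no source that is equal in both arms, and the incidental routes favor detection in PRO. Planned live calls are 1.8 to 2.3 times those of control if completed, mainly because of the roughly 20% who accept counseling. Most of PRO has at most one more scheduled conversation than control.

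A reader might go on to infer that recorded counts will certainly be higher in PRO. That does not follow from the documents. The direction is likely, but the size (1.2 to 1.5 in the illustration) rests wholly on assumed detection probabilities. Nor should a disclosure rate be multiplied by the number of calls to predict ideation counts, because one participant could then be counted many times. It is likewise an inference, not a stated rule, that deaths will go unnoticed; staff make repeated call attempts and have record access. What the text shows is that no step looks for deaths before imputation.

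The consequence is that counts of these events, gathered as described, could not be compared between arms. The imputation of the primary outcome also lacks a safeguard against treating the deceased as possible quitters.

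**What to change.** Extend the section 5.7.5 extract, for both arms and the same 12 months after enrollment, to dated VA hospitalizations, ER visits and deaths, and name it in section 8.0 as the source for these events. Tabulate them by randomized arm, including an early window such as the first three months, which contains the two-month call course. State in section 6.0 how a participant who died before month 12 is classified, and use the death data to do so before imputing non-respondents. Report events volunteered on calls, including suicidal ideation, in a separate table marked as not comparable between arms.

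The cost is small: extra fields in a pull that the same programmers already plan, apparently within the existing HIPAA waiver, plus one table. A single pull serves the final comparison; if the DSMB is to see counts during the trial, it must be repeated at set dates. The downsides are that non-VA events are missed in both arms, slightly more protected health information is abstracted, and suicidal ideation still has no source that is equal in both arms. No treatment or contact schedule changes.

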5.8 OUTCOMES

The primary outcome will be cotinine-validated abstinence from smoking at 12-month follow-up. Secondary outcomes include the following:

1. Self-reported 7-day abstinence (to estimate rates of misreporting) at 6 and 12 month follow-up.
2. Other cessation related outcomes at 6 and 12 months – e.g., quit attempts, cigarettes per day, cessation medication use, motivation, and self-efficacy.
3. Self-reported mental health distress and active substance abuse.

5.9 INFORMED CONSENT PROCEDURES

There are several levels of patient information and consent for this study, which are summarized in the table and discussed below.

| Category | Type of data | Approx. n | Authorization | Comments |
|--|--|-----------|--|--|
| 1. Health system users | Administrative data 
 • Smoking status • Mental Health clinic use • Phone number • Mailing address | 40,000 | HIPAA waiver | We will randomly select 20,000 from the EMR to contact via mail for possible enrollment |
| 2. All study participants | Survey data 
 • Baseline survey • Follow-up surveys Saliva sample Administrative data 
 • Utilization • Mental health diagnoses | 3,840 | Waiver of documentation of consent | Completing the baseline survey will serve as implied consent to the telephone follow-up surveys and saliva collection, to be contacted for counseling if in the Intervention arm, and to collect follow-up administrative data from the EMR. |
| 3. Intervention treatment participants | Intervention data 
 • Counseling information • Nicotine replacement preference | 384 | Verbal consent with a waiver of documentation of consent | Participants will provide verbal informed consent prior to enrolling in counseling |

Category 1: Health System Users. The proposed study will include men and women over the age of 18 years old who smoke and have had a Mental Health visit in the past 6 months. We will

request a HIPAA waiver to obtain a limited data set from the EMR to identify eligible subjects, which is necessary to carry out the study.

Category 2: All Study Participants. Patients who complete and return the baseline survey will be participants in the study. As indicated in the cover letter and FAQ sheet, their returning the survey implies they consent to participate and no written documentation of consent will be required. After receiving the baseline survey and verifying that the respondent is still smoking, we will randomize each person to either the intervention or control group.

Category 3: Intervention Arm Participants. Intervention participants will be offered telephone counseling. Prior to starting treatment, the counselors will discuss what each treatment involves and obtain verbal consent to proceed.

6.0 STATISTICS AND DATA ANALYSIS

Analysis

In the data analysis, we will focus on the analysis for inference in the subpopulation of smokers who respond to the baseline survey. The underlying assumption is that respondents to the baseline survey are comparable to non-respondents. With our proposed sample size, random assignment among subjects who returned baseline surveys stratified by hospital site can be expected to create two groups that are balanced with respect to observed and unobserved baseline characteristics. Balance of the two groups will be tested using Mantel-Haenszel χ^2 tests for categorical variables and appropriate parametric tests (e.g., Blocked Anova F-tests) or nonparametric tests (e.g., Wilcoxon rank-sum test). In addition, the data will be summarized numerically using descriptive statistics (means, medians, standard deviations, frequency distributions, and graphical displays including box plots) to characterize study participants in the two groups.

Missing Data

We anticipate low, but potentially important rates of survey non-response to all or part of the 6- and 12-month surveys. We will use the evidence-based recruitment strategies described above (incentives, reminders, mixed mode survey administration) to minimize non-response. A common practice in smoking cessation research is to treat non-respondents at follow-up as continuing smokers (i.e., intent to treat). This practice is perceived to be a conservative approach but does not, in fact, produce valid estimates of quit rates.³³ We will use multiple imputations to fully use available baseline information and partial later surveys. We will use a propensity-based multiple imputation method similar to that discussed by Little³⁴ using separate imputation procedures within each study group and design stratum combination. Within a given combination, we will estimate the propensity for responding to cotinine validated abstinence for each individual from a logistic regression model for survey response using the characteristics measured at baseline as explanatory measures. Within a combination of intervention and design strata, we will further stratify the sample according to the values for these estimated propensities. Within a propensity substratum, we will impute a value for the outcome measure for each non-respondent by randomly sampling an outcome value from the respondent values in the substratum. Multiple completed datasets will be created and the point estimates and the estimated standard error from each dataset will be combined to arrive at a single point estimate (using the specific method discussed below), its estimated standard error, and the associated confidence interval or significance test. This approach assumes that missing outcome data due to non-response is missing at random.

To assess the impact of non-ignorable survey non-response, or missing not at random non-response, we will implement pattern-mixture analyses. Using content expertise and the observed missing data patterns, we will develop these pattern-mixture models. The nature of these models is difficult to specify in advance of observing the different patterns but we will posit distributions for the missing data. For each set of posited distributions and the observed data, we will calculate revised estimates for the relevant intervention effects. One potential model would be to use the propensity stratum derived in the analysis described above and, within each stratum build a distribution for the outcome of interest by shifting the observed distribution among the responders. Content expertise and empirical results will be used to determine the form and magnitude of shift. These distributions would then be used to impute values for the non-responders to cotinine validation in the imputation process described immediately above. Variations of this approach and other approaches will be used to assess the sensitivity of the analyses above to non-ignorable non-response.

We will be enrolling patients after they complete the baseline survey, which maximizes our internal validity; thus we will have baseline data on all participants. The methods above for imputing missing data address the issue of non-response to all or part of either the 6-month or 12-month survey and cotinine validation. We will have limited data available on those who do not respond to the baseline survey, but we will use what data we have to compare initial responders to non-responders, in order to address external validity.

Specific aim analysis

The data will first be summarized numerically using descriptive statistics and frequency distributions examined for validity. Comparison of the baseline demographic and tobacco use characteristics between the two treatment groups will be performed using chi-square tests for categorical data and t-tests or nonparametric tests for ordinal or continuous data.

Aim 1: Compare the reach and efficacy of a proactive outreach telephone-based tobacco cessation (PRO) program for patients seen in mental health to usual care (UC) advice and referral to local VA and community tobacco cessation resources.

H1: Compared to the control group, the proactive intervention will increase the smoking abstinence rate at 12 month follow up.

Method: The study design is a randomized block design with the blocks comprising combinations of the four hospital sites.

We will address the question of Reach via two indices:

- Proportion of patients who respond to the outreach letters and enroll in the study (i.e., completed the baseline survey). This analysis will help us understand the proportion of smokers in Mental Health who will respond to proactive outreach. Given the innovative nature of the proactive outreach approach, we will examine the acceptability of the intervention to determine which patients are more likely to accept treatment in the PRO and UC conditions. Specifically, we will use multivariable logistic regression to determine which baseline characteristics (e.g., age, race/ethnicity, income, mental health diagnosis, symptom severity) are associated with receipt of cessation counseling (state quitline or VA) or use of cessation medications.
- Proportion of patients who engage in at least one treatment session compared to control patients. Specifically, we will determine how many patients in the intervention arm used treatment (counseling and/or medications) and compare this to the number of patients

enrolled in the control arm who report using existing VA tobacco cessation services on the follow-up surveys, which will provide data regarding acceptability of treatment.

The primary smoking outcome variable that is expected to be affected by treatment is dichotomous cotinine-validated abstinence at 12 months post-enrollment. The comparisons of the abstinence rates across the two groups will be made using exact logistic regression methods, accounting for stratification by site, to model the log odds of use of smoking cessation treatment and log odds of 12-month abstinence. Exact logistic regression employs the non-parametric Chi-square test or Fisher's exact test.³⁵ These tests are widely applicable in complete randomized experimental designs that yield contingency tables. Fisher's exact test is particularly suitable for contingency tables with small and unbalanced frequency counts, which are to be expected for the population-based outcome we have chosen where our population quit rate in the control condition is expected to be 4%.

Aim 2: Model longitudinal associations between baseline sociodemographic, medical and mental health characteristics and validated abstinence at 6 and 12 months in the PRO and UC conditions.

H2: We hypothesize that mental distress and active substance abuse are the strongest baseline predictors of treatment uptake and long-term abstinence in a mental health population.

Method: We will use a generalized linear mixed model approach³⁶ to determine smoking outcomes at 6 and 12 months. Following the recommended best practices in longitudinal data analysis,³⁷ we will use a two-level hierarchical linear model to fit the data. The outcome variable of interest will be the dichotomous cotinine-validated smoking abstinence data. Therefore, a logit model is appropriate at Level 1, where individual outcomes will be fitted for each subject using time as the primary covariate. The parameter estimates from these individual functions will then be entered as dependent variables in Level 2 in which treatment group (PRO vs. UC) is the covariate. This longitudinal analytic approach will help understand to what extent treatment effects differ between 6 and 12 months and whether they show a delayed effect (either increasing or decreasing over time). This will allow us to determine a treatment main effect as well as a treatment by time interaction. Baseline covariates will be included at the patient level (age, sex, race/ethnicity, nicotine dependence, motivation, self-efficacy, mental distress, and current substance use). Inclusion of covariates typically reduces residual errors and thus boosts statistical power as well as allows us to determine factors that affect abstinence to better target intervention design and content.

Power calculations

The power analysis is based on the primary outcome – cotinine-validated abstinence at 12-month follow-up. Our data is stratified on four hospital sites. Considering that a stratified random sample is usually more efficient than a simple random sample, to be conservative, we assume the two groups are two independent simple random samples in the following power analysis. Based on response rates during the first quarter of recruitment, we expect to receive completed surveys from 20-25% of the 20,000 patients receiving the initial mailing and 85% of respondents will be eligible (i.e., report smoking cigarettes in the prior 30 days). We will send initial mailings until we receive completed surveys from 3,840 eligible patients who will be randomly assigned to intervention and control and comprise the study population. We estimate the quit rate in the control group will be 4%. In the intervention group, about 20% of the people will accept our offer of telephone treatment, based on [name] data. We anticipate that the quit rate among Veterans

enrolled in counseling will be 16%. We are using a more conservative estimate from what we found in our recently-completed reactive recruitment study (20%) because participants will not have been directly referred from a healthcare provider. When the treatment cessation rate is combined with that from patients who do not accept treatment (assuming also a 4% quit rate), there will be a population-level quit rate of 6.4% in the intervention group, which gives us a 90% chance to detect a difference between the two groups.

The table below shows the detectable increases in anticipated long-term abstinence rate for the intervention group for power = 0.75, 0.80, 0.85, 0.90, based on two sided two independent proportions test with type I error of $\alpha=0.05$. We varied the anticipated long-term abstinence rate in the control group from 3% to 4%. (We used Pass 2008 NCSS software for the calculation.) As an example, the proposed sample size provides 80% power to detect any increase greater than 2.0% in population-level abstinence rate for the intervention group when the abstinence rate in the control group is 4%, a small but clinically-meaningful quit rate that results in overall cost-savings.³⁸ Reversing the calculation and solving for the quit rate for people who accept counseling, if the underlying quit rate is 4% and we get 20% of intervention patients to enroll in counseling (N=384), we will have 80% power to detect a difference if the success rate at counseling is as low as 14%.

Note that a lower response rate on the baseline survey does not affect our power. Since we randomize after response, we can mail additional surveys until we have 3,840 respondents. A recruitment cohort of 20,000 patients and enrolled sample of 3,840 participants therefore gives us some safety margin, to allow for variability in:

- The treatment engagement rate
- The rate of success at counseling (i.e., if less than 16%)
- If the success rate among intervention patients who do not enroll in counseling is <4% (which is conceivable, since these are the people who declined to enroll in telephone counseling).

Table 1: Statistical Power Analysis (1920 baseline survey respondents per group) for Abstinence Rates

| Control group P1 | Power | Intervention group P2 | Difference P2-P1 | Odds Ratio |
|------------------|-------|-----------------------|------------------|------------|
| 0.03 | 0.95 | 0.053 | 0.023 | 1.82 |
| 0.03 | 0.90 | 0.051 | 0.021 | 1.72 |
| 0.03 | 0.85 | 0.049 | 0.019 | 1.66 |
| 0.03 | 0.80 | 0.047 | 0.017 | 1.61 |
| 0.03 | 0.75 | 0.046 | 0.016 | 1.57 |
| 0.04 | 0.95 | 0.066 | 0.026 | 1.70 |
| 0.04 | 0.90 | 0.063 | 0.023 | 1.62 |
| 0.04 | 0.85 | 0.061 | 0.021 | 1.56 |
| 0.04 | 0.80 | 0.060 | 0.020 | 1.52 |
| 0.04 | 0.75 | 0.058 | 0.018 | 1.49 |

